7.8.4 Insulin Discontinuation Criteria

TN-10 Extension participants meeting insulin discontinuation criteria (defined as $\text{HbA1c} \leq 6.5\%$ and average daily insulin use ≤ 0.25 unit/kg/day) at each visit will be summarized, by prior TN-10 trial

treatment and overall. Only participants who have available HbA1c and insulin data at the relevant visit will be included in the summary.

7.8.5 Severe Hypoglycemic Episodes

Severe hypoglycemic episodes following the AESI definition in [Table 2](#) will be provided in a data listing.

7.8.6 Pharmacokinetics and Immunogenicity

Blood samples will be obtained on Days 1, 4, 9, 12 (before study drug infusion) and on Days 28, 182, and 364 to measure teplizumab trough levels, anti-drug antibodies, and neutralizing antibodies.

Teplizumab concentrations will be provided in a data listing on the PK analysis set.

The titers of anti-drug antibodies and presence of neutralizing antibodies will be measured in samples collected. Information including antibody titer will be provided in a data listing on the Immunogenicity analysis set.

7.8.7 Mechanistic Assessments

Details of the mechanistic assessments, including the secondary endpoint of assessing frequency of CD8+ TIGIT+ KLRG1+ T cells, will be provided in a separate mechanistic analysis plan.

7.9 Interim analysis

An interim analysis is not planned.

7.10 Changes in the statistical plans from those presented in the study protocol (if applicable)

- The protocol specifies the use of both an ITT and Safety analysis set. The SAP defines only the Safety analysis set as those participants who receive at least one dose of study drug.
- The frequency of CD8+ TIGIT+ KLRG1+ T cells will be part of a separate mechanistic analysis plan.
- The protocol specifies that comparisons will be made in C-peptide with historical controls. Due to the small number of patients enrolled in the TN-10 Extension study, these comparisons will not be performed as part of this SAP.
- The definition of adverse event of special interest (AESI) in the SAP is different from the study protocol and aligns with the AESI definition as agreed upon with FDA for the Integrated Summary of Safety (ISS) for the at-risk BLA approved in November 2022.

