10.3.3. Definition of AESI

The following types of AEs are considered AESIs:

- All infections: viral, fungal, bacterial
- Acute mononucleosis-like illness (eg, fever, pharyngitis, lymphadenopathy)
- CMV viremia defined using DNA PCR testing and >10,000 copies per mL serum or 10⁶ cells
- EBV viremia defined using DNA PCR testing and >10,000 copies per mL serum or 10⁶ cells
- Herpes zoster or other conditions related to VZV
- Primary infection with or reactivation of latent tuberculosis
- Infections requiring IV antibiotic treatment
- Demyelinating diseases
- Malignancies including lymphomas
- Severe hypoglycemic episodes that require assistance by another individual through the administration of oral or parenteral dextrose, glucagon or intervention
- ≥ Grade 3 liver function abnormalities (AST, ALT, bilirubin)
- ≥ Grade 3 thrombocytopenia (platelet counts less than 50,000/µL)
- ≥ Grade 3 allergic/hypersensitivity reaction (anaphylaxis)
- ≥ Grade 3 Rash

- \geq Grade 3 cytokine-release syndrome
- \geq Grade 4 neutropenia (<500 PMN/ μ L on 2 consecutive evaluations performed on different days)

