These events will be captured on the CRF and reported to the Sponsor as described in Section 8.4.1.1. Any event that meets serious adverse event criteria will be reported to the Sponsor within the appropriate timeline as described in Section 8.4.1.4.

Events will be assessed and reported consistent with the ICH Guideline for Good Clinical Practice and per the guidance of the DHHS Office for Human Research Protections (OHRP).

Event outcome and other follow-up information regarding the treatment and resolution of the event will be obtained and reported when available, if not known at the time the event is initially reported. The follow-up information should contain sufficient detail to allow for a complete medical assessment of the case and an independent determination of possible causality.

AESIs should be reported according to the requirements for SAEs.

Assessment of Severity

An assessment of severity grade for each AE will be made by the site Investigator according to the criteria set forth in the National Cancer Institute's Common Terminology Criteria for Adverse Events Version 5.0. This document (referred to herein as the "CTCAE V5.0") provides a common language to describe levels of severity, to analyze and interpret data, and to articulate the clinical significance of all AEs. The Investigator should use clinical judgment in assessing the severity of events not directly experienced by the participant (eg, laboratory abnormalities).

Adverse events will be graded according to National Cancer Institute (NCI) Common Terminology Criteria for Adverse Events (CTCAE) version 5.0:

- Grade 1 = Mild adverse event.
- Grade 2 = Moderate adverse event.
- Grade 3 = Severe adverse event.
- Grade 4 = Life-threatening or disabling adverse event.
- Grade 5 = Death

Assessment of Causality

The Investigator is required to provide an assessment of causality or relationship of adverse events to the study drug based on 1) temporal relationship of the event to the administration of study drug; 2) whether an alternative etiology has been identified; and 3) biological plausibility. The causality assessment categories that will be used for this study are described below.

Causality assessments considered **not** related to study drug:

- Unrelated: The event is related to an etiology other than the study drug (the alternative etiology must be documented in the participant's medical record).

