2 STUDY OBJECTIVES AND ENDPOINTS

Objectives and Endpoints

Objectives	Endpoints
Primary	

 To evaluate the safety and tolerability of teplizumab treatment, administered intravenously (IV) to participants in the TN-10 trial who have developed T1D. 	
 Incidence of treatment-emergent adverse events (TEAEs), adverse events of special interest (AESIs), and serious adverse events (SAEs)
Secondary	

 To evaluate the pharmacokinetics (PK) and immunogenicity of teplizumab 	
 Levels of teplizumab in the serum and anti-drug antibodies

 To evaluate whether teplizumab treatment reduces the loss of β cells, over 78 weeks (18 months), in individuals with recent diagnosis of T1D. 	
 The area under the time-versus-concentration curve (AUC) of C-peptide after a 4-hour (4h) mixed-meal tolerance test (MMTT), a measure of endogenous insulin production and β cell function, over 78 weeks

 To evaluate key clinical parameters of diabetes management, including insulin use, hemoglobin A1c (HbA1c), and clinically important hypoglycemic episodes over 78 weeks 	
 HbA1c levels; insulin use, defined as a daily average dose in units per kilogram per day (U/kg/day); and frequency of clinically important hypoglycemic episodes over 78 weeks

 To evaluate whether treatment with teplizumab increases the frequency of exhausted T cells 	
 Frequency of CD8+ TIGIT+ KLRG1+ T cells

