7.7.1 Adverse events

Adverse events will be coded using the latest version of MedDRA applicable at the time of database lock.

A treatment emergent adverse event (TEAE) is defined as an adverse event which starts during or after the first dose of teplizumab. If an adverse event occurring the same day as the first dose of teplizumab cannot be determined to occur before or after the dosing begins, it will be assumed to be treatment emergent.

Adverse event severity is assigned according to the National Cancer Institute CTCAE v5.0. In the case of summaries by CTCAE grade, the highest grade experienced by the participant will be used for the reporting category.

Relationship of an adverse event to study treatment will be considered as "Related" in tabular summaries if the options of "Possible", "Probable", or "Definite" are selected for the adverse event in the eCRF. Options of "Unrelated" or "Unlikely" will be considered as "Not Related".

An adverse event is defined as an Adverse Event of Special Interest (AESI) if it meets any of the following criteria:

- All \geq Grade 3 infections (includes all opportunistic infections): viral, fungal, bacterial
- Acute mononucleosis-like illness (e.g., fever, pharyngitis, lymphadenopathy, clinical EBV and CMV infections and reactivations)
- Malignancies including lymphomas
- Severe hypoglycemic episodes
- \geq Grade 3 liver function abnormalities (AST, ALT, bilirubin), i.e., an AST or ALT value $>5.0 \times$ ULN or a bilirubin value $>3.0 \times$ ULN
- \geq Grade 3 thrombocytopenia (platelet counts less than 50,000/ μ L)
- \geq Grade 3 neutropenia (<1000 PMN/ μ L on 2 consecutive evaluations performed on different days)
- \geq Grade 4 allergic/hypersensitivity reaction (anaphylaxis)
- \geq Grade 3 Rash
- \geq Grade 4 cytokine-release syndrome
- Lymphocyte count $<500/\text{mm}^3$ for 7 days or longer

Table 2 The Search Criteria for AESI

AESI	Search Criteria
\geq Grade 3 infections (will include all opportunistic infections)	SOC – 'Infections and Infestations'; \geq Grade 3
Acute mononucleosis-like illness (e.g., fever, pharyngitis, lymphadenopathy)	PT – 'Mononucleosis syndrome', 'Epstein-Barr virus antibody positive', 'Epstein-Barr virus test positive', 'Epstein-Barr viremia', 'Cytomegalovirus antibody positive', 'Cytomegalovirus test positive', 'Infectious mononucleosis', 'Lymphadenopathy', 'Epstein-Barr virus infection', and 'Cytomegalovirus infection'

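### The SAP replaces the protocol's AESI definition, part of the primary endpoint, with a different one (narrower in some criteria, broader in others) and plans no analysis on the protocol definition

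*SAP*

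**What the plan says.** Protocol section 3 and SAP section 2 give the same primary endpoint: the incidence of treatment-emergent adverse events (TEAEs), AESIs and serious adverse events. Protocol 10.3.3 defines the AESIs. Its list opens with "All infections: viral, fungal, bacterial", has a separate entry for "Herpes zoster or other conditions related to VZV", and sets cytokine-release syndrome (CRS) and hypersensitivity at Grade 3 or higher. Protocol 10.3.4 adds that "AESIs should be reported according to the requirements for SAEs".

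SAP 7.7.1 and its Table 2 set out another list. Infections must reach Grade 3. CRS enters at "Grade 4 cytokine-release syndrome" or above, and hypersensitivity is also raised to Grade 4. SAP 7.10 declares the replacement ("The definition of adverse event of special interest (AESI) in the SAP is different from the study protocol") and explains it as following a definition agreed with FDA for the integrated summary of safety (ISS) of the at-risk BLA approved in November 2022. It does not say which criteria changed.

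The only AESI outputs in SAP 7.7.1 are a line in the overall summary, one table by AESI category and preferred term, and one listing. All use the SAP list.

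**The concern.** The endpoint label is the same in both documents, but what it counts has changed. A reader who compares the study report with the protocol will see an AESI incidence and take it to be the protocol's, and no planned output would allow the protocol's figure to be read off.

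What drops out matters for this trial. Protocol 4.2 says that, for participants treated in TN-10, the gap between courses is longer than any tested so far and the effect of anti-drug antibodies is unknown. Hypersensitivity and CRS are natural things to watch in that setting. Under the SAP, a Grade 3 case of either would not be identified as an AESI.

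**Working it through.** The plan states no figure to reproduce: the study is descriptive and its sample size has no formal basis. The check is a comparison of the two lists, followed by a rough look at direction.

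**Comparison of protocol 10.3.3 with SAP 7.7.1 and Table 2**

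| Criterion | Protocol | SAP | Direction |
|---|---|---|---|
| Infections | Any grade | Grade 3 or higher | Narrower |
| Zoster/VZV, tuberculosis, infections needing IV antibiotics | Own entries, any grade | No own entry; count through the Grade 3 infection search | Narrower (same change as the row above) |
| CMV and EBV viremia | PCR above 10,000 copies | No threshold; EBV viremia and EBV/CMV test-positive, antibody-positive and infection terms count at any grade; no CMV viremia term | Threshold lost; most reported events kept |
| Demyelinating disease | Listed | Absent | Dropped |
| Hypersensitivity | Grade 3 or higher | Grade 4 or higher | Narrower |
| CRS | Grade 3 or higher | Grade 4 or higher | Narrower |
| Neutropenia | <500/µL | <1000/µL | Broader |
| Lymphocytes <500/mm³ for at least 7 days | Absent | Listed | New |
| Malignancy | Malignancies, lymphomas | Search also takes benign terms | Broader |
| Rash | Grade 3 or higher | Grade 3 or higher, searched over the whole skin class | Same grade, wider search |
| Liver, platelets | Grade 3 or higher | Grade 3 or higher | Same grade |

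One entry is ambiguous. The SAP's infection criterion says in parentheses that it includes all opportunistic infections. That could mean at any grade, but the Table 2 search limits the whole infection class to Grade 3 or higher and names no opportunistic or zoster term.

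**Direction of the total.** The SAP maximum is 30. Actual enrolment is not given, and SAP 7.10 calls it small, so 10 and 30 are both shown.

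- Infection, TN-10 (protocol Table 2): related infections in 5 of 44 = 11.4%. Expected: 10 × 5/44 = 1.1; 30 × 5/44 = 3.4. All are AESIs under the protocol. Under the SAP only those at Grade 3 or higher count, and the grade split is not given. Unrelated infections would add to the protocol count.
- Lymphopenia, TN-10 (protocol 2.3): 15 Grade 3 events, shown as 34.1%, which matches 15/44. Expected: 10 × 15/44 = 3.4; 30 × 15/44 = 10.2. None is an AESI under the protocol. Under the SAP these are upper bounds, because the share lasting 7 days is not reported.
- CRS, Protégé (protocol 2.3): about 6% at any grade. Expected: 10 × 0.06 = 0.6; 30 × 0.06 = 1.8. The protocol calls CRS usually mild to moderate, so the Grade 3 part, which is what the SAP loses, is an unstated fraction of this.

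The narrowed criteria lower the count and the new ones raise it, by amounts that the documents do not fix. The sign of the net change is unknown.

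**What remains visible.** The tables by system organ class and preferred term are not split by grade; grade appears only in the overall summary. A Grade 3 CRS would share a row with Grade 1 CRS and would have to be picked out of a listing. EBV and CMV PCR results are listed in IU/mL (SAP 7.7.6), whereas the protocol threshold is in copies, so it cannot be applied to the listing directly.

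**The case against.** The case for leaving the SAP alone has real weight. The change is declared, with a reason: it "aligns with the AESI definition as agreed upon with FDA for the Integrated Summary of Safety (ISS"). Protocol 9.4.1 leaves safety details to the SAP, and protocol 4.3 foresees combining these data with other studies, for which a common definition helps. Nothing is tested. Every TEAE is tabulated and listed, and serious ones have their own tables. In a small single-arm study a reader can inspect each event. All of this stands, and it limits the severity. It does not supply the AESI incidence that the protocol defined.

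Several stronger readings are tempting but unsupported.

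- A reader might call the new definition simply narrower, or count nine of the protocol's sixteen entries as lost. That overlooks the criteria that were widened or added. It also counts one infection change four times, since zoster, tuberculosis and IV-antibiotic infections already sit within all infections, and it treats EBV viremia as lost when only the threshold is.
- A reader might say the Grade 4 rows will be zero by construction. TN-10 had 0 of 44 teplizumab participants with a related Grade 4 event (upper 97.5% limit 1 − 0.025^(1/44) = 8.0%), so empty rows are likely. But no Grade 3 rate for CRS or hypersensitivity is given, so the rows might be nearly empty under either rule.
- A reader might think serum sickness has been removed. Protocol 10.3.3 does not name it; the SAP search adds the term, at Grade 4.
- A reader might object that the ISS concerns another disease stage. The documents do not say which studies it pooled, and protocol 2.3 says much of the teplizumab safety experience is in Stage 3.
- A reader might suspect that results guided the choice, since the study is open-label and the version 1.0 entries run from October 2023 to February 2024. The cited source is tied to an approval in November 2022, and nothing in the documents shows that this trial's data played a part.

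**Conclusion.** The concern holds in this form: a component of the primary endpoint is redefined, and no planned output reports it as the protocol defined it. The loss is specific for infections below Grade 3 (on the Table 2 search, including zoster), Grade 3 CRS, Grade 3 hypersensitivity, demyelinating disease and the viremia thresholds. The net effect on the AESI total cannot be signed.

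The expected counts rest on TN-10 and Protégé rates carrying over to this trial. TN-10 used a 14-day course in an earlier disease stage, and Protégé gave two courses. The counts indicate direction only.

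Because the change is declared, the events stay in the TEAE outputs and there is no test to distort, this is a cheap improvement and not a must-fix.

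**What to change.** In SAP 7.7.1, keep the present AESI table and label it as ISS-aligned. Add one table and one listing on the protocol 10.3.3 definition, reported as the protocol-defined AESI component of the primary endpoint. For that table, give search terms for zoster/VZV, tuberculosis, infections needing IV antibiotics and demyelinating disease, and state how PCR results in IU/mL map to the protocol's threshold in copies.

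In SAP 7.10, list each criterion removed, narrowed, widened or added, and say whether the parenthesis on opportunistic infections means any grade.

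The cost is one extra table and listing plus some search-term and unit-conversion work. Sites were already asked to report protocol AESIs under the serious-event requirements, so no new safety reporting should be needed. The protocol-defined count will include mild infections and may look high. Showing both tables, with the changes itemised in 7.10, lets readers see why.

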7.11 Execution of statistical analyses

Statistical analysis will be performed by IQVIA Biotech under the supervision of Provention Bio, Inc. and Sanofi.

8 HARDWARE AND SOFTWARE

Statistical analysis, tables, figures, and participant data listings will be performed with SAS® for Windows version 9.4 or higher (SAS Institute Inc., Cary, NC, USA).

10 APPENDICES

None

11 DOCUMENT HISTORY

Version number	Version date	Author	Comments
0.1	17MAR2021	[REDACTED]	N/A – First version

0.2	24MAY2023	[REDACTED]	Updated to clarify most presentations would be data listings due to expected enrolment.
1.0	25OCT2023	[REDACTED]	Updated per PRVB team review
1.0	18JAN2024	[REDACTED]	Finalization of SAP text per 2 nd team review
1.0	21FEB2024	[REDACTED] [REDACTED]	Minor editorial changes prior to signature of V1.0.
